7.6 Concomitant Medications

All concomitant medications listed on the case report form will be provided in data listings in the clinical study report. Each medication will be mapped to their corresponding Preferred Term from the WHO Drug Dictionary. A frequency distribution of all concomitant medications used during the study sorted by Preferred Term will be provided for each treatment group.

7.7 Ocular and Other Medical History

Ocular and other medical history reported at the Screening Visit and on Day 0 prior to the first dose of study drug, will be summarized by System Organ Class and Preferred Term.

7.8 Clinical Laboratory Assessment

Clinical laboratory data (hematology, serum chemistry, and urine) at each scheduled visit will be summarized with descriptive statistics by treatment group, as will the change from baseline to each post-baseline visit. Each subject's data will also be classified to low, normal, and high according to the normal ranges. These data will be summarized in shift tables comparing each post-baseline visit to baseline.

7.9 Physical examination

Physical examination findings at the Screening Visit will be summarized by System Organ Class and Preferred Term.

7.10 Vital Signs

Descriptive statistics of vital signs and their change from baseline will be tabulated by time point and treatment group.

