IP Administration in Office		X Unilateral post T ₀ + 12 hrs IOP	X Unilateral post IOP	X OU post IOP	X OU post T ₀ and T ₀ + 12 hrs IOP	X OU post T ₀ IOP (final dose)
Assess IP Compliance				X	X	X
Heart Rate/Blood Pressure (± 30 min)	X	X Pre-T ₀ T ₀ + 1 hr T ₀ + 2 hrs T ₀ + 4 hrs				X Pre-T ₀ T ₀ + 1 hr T ₀ + 2 hrs T ₀ + 4 hrs
ECG	X					
Physical Examination	X					
Best-corrected Visual Acuity (ETDRS)	X	X Pre-T ₀	X	X Pre-T ₀	X Pre-T ₀	X Pre-T ₀
Biomicroscopy ³ (± 30 min)	X	X T ₀ T ₀ + 2 hrs T ₀ + 4 hrs T ₀ + 8 hrs T ₀ + 12 hrs	X Pre-T ₀	X Pre-T ₀	X Pre-T ₀	X Pre-T ₀ T ₀ + 2 hrs T ₀ + 4 hrs T ₀ + 8 hrs T ₀ + 12 hrs
Pupillary Diameter (± 30 min)		X Pre-T ₀				X Pre-T ₀
Conjunctival Hyperemia Grading (± 30 min)		X T ₀ T ₀ + 2 hrs T ₀ + 4 hrs T ₀ + 8 hrs T ₀ + 12 hrs		X Pre-T ₀	X Pre-T ₀	X Pre-T ₀ T ₀ + 2 hrs T ₀ + 4 hrs T ₀ + 8 hrs T ₀ + 12 hrs

¹ When possible, one examiner should conduct all ocular assessments for a subject during a single visit. If possible, the same examiner should conduct all ocular assessments for a subject throughout the duration of the study.

² +1 week permitted to accommodate scheduling considerations

³ If any adverse findings are noted after IP administration, the subject should continue to be monitored per the investigator's judgment.

Assessments/Procedures ¹	Screening (-42 ² to -1 days)	Day 0 Baseline/ Randomization	Day 1	Day 4 (± 1 day)	Day 14 (± 1 day)	Day 28 Exit/ET (± 2 days)
Intraocular Pressure ⁴ (Goldmann Tonometry) (± 30 min)	X	X T ₀ T ₀ + 1 hrs T ₀ + 2 hrs T ₀ + 4 hrs T ₀ + 8 hrs T ₀ + 12 hrs	X T ₀	X T ₀ T ₀ + 1 hr T ₀ + 2 hrs T ₀ + 4 hrs T ₀ + 8 hrs T ₀ + 12 hrs	X T ₀ T ₀ + 1 hr T ₀ + 2 hrs T ₀ + 4 hrs T ₀ + 8 hrs T ₀ + 12 hrs	X T ₀ T ₀ + 1 hr T ₀ + 2 hrs T ₀ + 4 hrs T ₀ + 8 hrs T ₀ + 12 hrs
Pachymetry ⁵	X					
Gonioscopy ⁶	X					
Visual Fields (automated, threshold)	X ⁷					
Dilated ophthalmoscopy	X					X ⁸
Blood Collection for PK of H-1337 (± 10 min at 2 & 8 hrs)		X				X Pre-T ₀ T ₀ + 2 hrs T ₀ + 8 hrs
Clinical Laboratories (hematology, clinical chemistry, pregnancy (if applicable), and urinalysis)	X ⁹	X ¹⁰				X ¹¹

⁴ Timing of IOP measurements for each subject should be consistent throughout the study.

⁵ Pachymetry performed at screening will be used for inclusion/exclusion criteria only. Pachymetry within 6 months of Screening acceptable unless suspected change.

⁶ Gonioscopy within 6 months of Screening acceptable unless suspected change.

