5 STUDY VISIT PROCEDURES

All study visit procedures should be conducted in the order listed [Section 5.1](#).

Informed Consent: Properly executed informed consent (written and verbal) is to be obtained prior to completion of any study-related procedures. Subjects must review, sign, and date the informed consent document and receive a copy.

Medical and Ophthalmic History: Relevant and clinically significant medical and ophthalmic history must be recorded.

Concomitant Medications: All prescription and over-the-counter (OTC) medications and nutritional supplements taken during the study and 30 days prior to the Screening Visit will be recorded. Diagnostic eye drops do not need to be recorded.

Randomization: Randomization will be accomplished using an Interactive Web Response System (IWRS). Site personnel will receive instruction about IWRS access and use.

Adverse Events: Any events occurring after the first dose of IP will be recorded as an adverse event. At each visit, the subject should be asked questions such as, "How are you feeling? How are your eyes feeling today? Have you had any changes since the last exam?"

IP Administration and Compliance: The first dose of study IP will be administered to the study eye by study staff after the IOP measurement at T0 + 12 hrs. At Day 1/Visit 3 the AM dose of study IP will be administered to the study eye by study staff after the IOP measurement at T0. Subjects will self-dose unilaterally until the Day 4 visit. At Day 4/Visit 4 the AM dose of study IP will be administered OU by study staff after the IOP measurement at T0. Subjects will self-dose OU for the remainder of the trial except on Day 14/Visit 5 (AM and PM doses) and Day 28/Visit 6 (AM dose) when study IP will be administered OU by study staff after the related IOP measurements. Compliance will be assessed at applicable visits by asking the subject about any missed doses. If the subject reports missing more than 4 doses since the prior visit, the subject will be counseled on IP compliance.

Heart Rate and Blood Pressure (BP) Measurements: Both systolic and diastolic blood pressure should be recorded. The same type of device and cuff must be used throughout the study on the same subject. An appropriate cuff size with a bladder encircling at least 80% of the upper arm should be used to ensure accurate measurements.

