2.3 Study Design/ Procedures

The study will evaluate the safety, tolerability, and preliminary efficacy of 3 concentrations of H-1337 and vehicle administered twice daily for 28 days. Up to 100 subjects, naïve to H-1337, will be randomized and dosed for 28 days. The parallel group, double-masked, placebo-controlled study will include the following dosing cohorts:

H-1337 0.06% (n=20)

H-1337 0.2% (n = 20)

H-1337 0.6% (n = 20)

Control (Vehicle) (n = 20)

Dosing will be BID unilaterally in the study eye for the first 3 days, then BID OU from Day 4 to Day 28.

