7. STATISTICAL ANALYSIS

All statistical analyses and reporting will be performed using the SAS® System Version 9.3 or later.

Unless otherwise specified, continuous variables will be summarized with descriptive statistics (n, mean, median, standard deviation, standard error, minimum, and maximum), and categorical variables will be summarized with counts and percentages.

All data collected in the study database will be presented in the listings.

Definition of Study Eye: The study eye will be the eye that meets the entry intraocular pressure (IOP) criteria after washout. Should both eyes meet the criteria, then the study eye will be defined as the eye with the higher 8 am IOP on Baseline (Day 0). If both eyes have the same 8 am IOP on Baseline (Day 0), the study eye will be the right eye. The study eye will be designated by the investigator. The designation may take into account ocular history as well as IOP criteria.

Definition of Baseline:

For vital signs, PK, BCVA and biomicroscopy baseline is the pre-T0 time point on Day 1. For clinical laboratories and pupil diameter baseline is the Day 0 collection. For IOP and hyperemia baseline is the set of repeated measures at different times during the Day 0 visit. For ophthalmoscopy baseline is the Screening Day.

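### The SAP's vital-sign baseline names a visit with no reading, and moving it to Day 0 pre-T0 alone would leave any time-of-day drift in each arm's Day 28 post-dose change

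*SAP*

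**What the plan says.** The baseline definitions are in SAP section 7. For vital signs: "For vital signs, PK, BCVA and biomicroscopy baseline is the pre-T0 time point on Day 1". Two other measures are handled differently in the same paragraph: "For IOP and hyperemia baseline is the set of repeated measures at different times during the Day 0 visit".

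The Schedule in the protocol and its copy in SAP Appendix 1 agree on when heart rate and blood pressure are taken after screening. On both Day 0 and Day 28 the entry is "Pre-T ₀ T ₀ + 1 hr T ₀ + 2 hrs T ₀ + 4 hrs". The cells for Days 1, 4 and 14 are empty.

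Protocol section 5 says the first dose, on Day 0, is "administered to the study eye by study staff after the IOP measurement at T0 + 12 hrs". On Day 28 the in-office dose follows the T0 pressure measurement.

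SAP 7.10 is a single sentence: "Descriptive statistics of vital signs and their change from baseline will be tabulated by time point and treatment group". It gives no time-matching rule, no difference from vehicle and no interval.

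**The concern.** There are two faults in one definition.

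The first is that the named baseline does not exist. No heart rate or blood pressure is scheduled on Day 1, and by that morning the subject has already had a dose. Read literally, the change from baseline cannot be computed for these measures.

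The second would survive the obvious repair. If only the day is corrected, one early-morning value becomes the baseline for readings taken up to four hours after T0. Anything that moves heart rate or blood pressure between those times without drug, such as time of day, rest or repeated examination, would then be included in the tabulated change. The Day 0 visit supplies undosed readings at the same hours, which would take this out.

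Systemic safety is part of the primary objective, and this is the first use of the compound in humans. ECG and physical examination are scheduled at Screening only. The Day 28 heart rate and blood pressure series is therefore the only scheduled on-treatment cardiovascular measurement, and its change column should be readable without a correction made by eye.

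**Working it through.** The plan states no figure for vital signs, so there is none to reproduce. The check rests on timing and a short piece of algebra.

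**Timing.** T0 is 8 am ± 30 min (protocol 4.1).

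| Reading | Day 0 | Day 28 |
|---|---|---|
| Pre-T0 | undosed | before that morning's dose |
| T0 + 1, + 2, + 4 h | undosed (first dose follows T0 + 12 h) | after that morning's dose |

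All four Day 0 readings precede any dose, and each has a Day 28 partner at the same clock time. Under a Day 0 pre-T0 baseline, three of the four would not serve as baseline.

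**Algebra.** Let μ be the undosed mean at pre-T0, d the drift from pre-T0 to T0 + k (taken to be the same on both days), and δ the drug effect at T0 + k on Day 28.

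- Change from Day 0 pre-T0: (μ + d + δ) − μ = d + δ
- Change from Day 0 T0 + k: (μ + d + δ) − (μ + d) = δ
- Active minus vehicle, pre-T0 baseline: (d + δ) − d = δ
- Active minus vehicle, matched baseline: δ − 0 = δ

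The single baseline adds d to every arm's change. The between-arm difference is the same in expectation under either baseline.

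**Simulation with no drug effect.** The settings were n = 20 per arm (from the plan) and 20,000 replicates. The between-subject SD of 12, within-subject SD of 6 and the values of d are assumptions, not figures from the documents.

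| Assumed d | Change, pre-T0 baseline | Change, matched baseline | Active − vehicle, pre-T0 | Active − vehicle, matched |
|---|---|---|---|---|
| −5 | −4.99 | 0.01 | 0.01 | 0.00 |
| −3 | −3.01 | 0.00 | −0.02 | −0.02 |
| 0 | 0.00 | 0.00 | −0.01 | −0.01 |
| +3 | 2.99 | 0.01 | −0.05 | 0.01 |
| +5 | 5.02 | −0.01 | 0.02 | −0.02 |

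**Scale.** With these assumed SDs, either change has SD 6 × √2 = 8.49 per subject, so the standard error of an arm mean is 8.49/√20 = 1.90. A drift of 3 to 5 units is then 3/1.90 = 1.6 to 5/1.90 = 2.6 standard errors within an arm. Time matching costs no precision in this set-up, because both changes have the same SD.

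**Limit.** Time matching removes clock-time drift only. A general shift between the Day 0 and Day 28 visits, such as familiarity with the clinic, stays in the within-arm change under either baseline. Only comparison with vehicle removes that.

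**The case against.** The strongest reply is that the trial is randomised and masked with a concurrent vehicle arm, and SAP 7.10 tabulates by treatment group. The same drift appears in the vehicle column of the same table, so anyone comparing active with vehicle is not misled in expectation. This stands, and the table above confirms it. A reader might infer that the safety comparison of drug with vehicle is biased, or that drift would be reported as a drug effect. The documents do not support either reading.

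Second, SAP 7.10 summarises the observed values as well as the changes, by time point. Protocol 8.2 likewise asks for observed and change values at each visit and time of day as appropriate. The undosed Day 0 means at the later hours should therefore be in the tables. A reader could see any drift, and could subtract to get the mean matched change if the same subjects contribute at both visits. This also stands. What would be missing is the SD of the matched change, and the printed change column would still contain the drift.

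Third, the size is entirely assumed. The standard-error figures above also use a within-arm yardstick for which the SAP plans no test. Both points are accepted.

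Fourth, only the IOP endpoints are required by the protocol to be compared at matched times. A different baseline for vital signs is a choice, not a contradiction. That is correct for time matching. It does not rescue the Day 1 reference, which conflicts with both schedules.

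Finally, the Day 0 procedure list in protocol 5.1.2 omits heart rate and blood pressure. This is minor, because 5.1 refers sites to the Schedule, which includes them.

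**Conclusion.** The point holds in a limited form. The Day 1 baseline is an error: neither schedule has a heart rate or blood pressure reading on that visit, and it follows the first dose. If the repair goes no further than Day 0 pre-T0, each arm's post-dose change on Day 28 would equal drug effect plus time-of-day drift, unit for unit. Over an assumed drift of −5 to +5 units, the spurious within-arm change is −5 to +5. The true size and sign cannot be obtained from the documents. Full cancellation by matching assumes the same drift on Day 0 and Day 28.

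The randomised contrast is sound in expectation under either Day 0 baseline. What remains is that the plan does not call for that contrast to be presented, so the tabulated change is within-arm and mixes two things that data already scheduled could separate. This is a low-priority improvement at no data cost, worth making because the same sentence must be corrected anyway.

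**What to change.** In SAP section 7, take vital signs out of the Day 1 sentence. Define the heart rate and blood pressure baseline for each Day 28 time point as the Day 0 value at the same time point, in line with the repeated Day 0 baseline already used for IOP and hyperemia. State in SAP 7.10 that the tabulated change is time-matched in this way. The other measures in the Day 1 sentence need their own check against the schedules.

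Two additions are optional:

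- Show the active-minus-vehicle difference in time-matched change for each concentration, with a 95% confidence interval labelled as descriptive.
- List heart rate and blood pressure in protocol 5.1.2 so that the Day 0 list agrees with the Schedule.

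The cost is a few lines of SAP text, plus one line in the protocol if the second addition is taken. No visit, measurement or sample is added. The SAP changes should be made before database lock and unmasking.

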7.11 Electrocardiogram

The interpretation of the ECG with respect to normal/abnormal will be tabulated.

7.12 Best-Corrected Visual Acuity

Descriptive statistics of the observed and change from baseline BCVA will be tabulated for each eye by visit and treatment group.

7.13 Ocular Hyperemia, Biomicroscopy, Ophthalmoscopy and Ocular Symptoms

The observations of ocular hyperemia, biomicroscopy, ophthalmoscopy, and ocular symptoms will be summarized in frequency tables based on the ordinal scales for each measure for each eye by time point and treatment group. In addition, the photographic assessment of ocular hyperemia will be summarized by descriptive statistics (See Appendix 2).

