8.2 Statistical Methods

Continuous and ordinal measures will be summarized by descriptive statistics (n, mean, standard deviation, median, minimum and maximum values). Qualitative measures will be tabulated by counts and percentages. Selected safety measures may be summarized by the use of shift tables. Summary tables will show the data for each time point (visit and/or time of day as appropriate) and will display the observed and change (and for IOP the % change) from baseline value.

A statistical analysis plan will be prepared prior to unmasking the treatment assignments.

An analysis of results will be conducted when the database for each stage has been locked and the treatment assignments have been revealed. No within-stage interim analyses are planned.

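### SAP 7.13 tabulates the ordinal slit-lamp and optic nerve grades only as frequencies at each time point, so the planned summary tables cannot show how many subjects worsened in grade

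*SAP*

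**What the plan says.** **Planned output.** SAP 7.13 covers ocular symptoms, the hyperemia grade, and the slit-lamp and fundus examinations. It says that all of these "will be summarized in frequency tables based on the ordinal scales for each measure for each eye by time point and treatment group". It makes one addition: "In addition, the photographic assessment of ocular hyperemia will be summarized by descriptive statistics (See Appendix 2". Appendix 2 then gives change from Day 0 for that photographic hyperemia grade. Nothing further is planned for the slit-lamp or fundus grades.

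**Protocol rule.** Protocol 8.2 states: "Continuous and ordinal measures will be summarized by descriptive statistics (n, mean, standard deviation, median, minimum and maximum values". It goes on to say that the summary tables, by visit or time of day, "will display the observed and change (and for IOP the % change) from baseline value". Qualitative measures are to be given as counts and percentages. Shift tables are optional: "Selected safety measures may be summarized by the use of shift tables".

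**Baselines.** SAP section 7 states "For vital signs, PK, BCVA and biomicroscopy baseline is the pre-T0 time point on Day 1" and "For ophthalmoscopy baseline is the Screening Day".

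**Other safety measures in the SAP.** Change from baseline is planned for vital signs (7.10), visual acuity (7.12), pupil diameter (7.14) and laboratory data (7.8). For the laboratory data the SAP adds: "These data will be summarized in shift tables comparing each post-baseline visit to baseline".

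**Adverse events.** Under dilated ophthalmoscopy (Protocol section 5, SAP section 3), a new fundus finding or a worsening since Screening must be reported as an adverse event. Protocol 7.2 and 7.3 make clinically significant signs and certain abnormal test findings reportable, and exempt findings that the investigator judges not clinically significant. SAP 7.5 tabulates events by preferred term and counts an event in both eyes once.

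**The concern.** The slit-lamp signs (lid erythema and edema, conjunctival hyperemia and edema, corneal edema, cells, flare, lens opacity) and the optic nerve grade are ordinal scales. Under Protocol 8.2 their summaries should include change from baseline. The SAP provides this for the other repeated safety measures and for the photographic hyperemia grade, but not for these. It defines a baseline for each of the two examinations and then makes no use of it in 7.13.

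Some signs will be present before treatment. The entry criteria accept mild blepharitis, lens opacity is graded in every phakic eye, and optic nerve damage is to be expected in subjects with open angle glaucoma. A frequency at a visit mixes old findings with new ones, and improvement in some eyes can offset worsening in others.

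Local ocular safety is part of the primary objective. The natural question is how many subjects in each arm got worse on each sign, and the planned summary tables do not answer it.

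**Working it through.** No sample size, power or alpha figure is at issue, so there is no figure of the plan to reproduce. The check is whether the number who worsened can be recovered from two frequency tables.

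**Inputs.** n = 20 per arm (SAP section 4). One eye per subject, the study eye, so that eyes and subjects coincide. All 20 are assumed to be examined at both visits. The grade counts are assumptions chosen for illustration; the documents give none.

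**Formula for a sign scored 0 or 1.** Let a be the number affected at baseline, b the number affected at Day 28, w the number going from 0 to 1 and r the number going from 1 to 0. Then b = a + w − r, so the two tables fix only the difference w − r = b − a. The range for w is

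max(0, b − a) ≤ w ≤ min(n − a, b).

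**Results.**
- a = 6, b = 6: from max(0, 0) = 0 to min(14, 6) = 6. Six is 6/20 = 30% of the arm, or 6/14 = 43% of the 14 eyes that were clear at baseline.
- a = 10, b = 10: from 0 to min(10, 10) = 10.
- Grades 0/1/2/3 counted as 14/6/0/0 at baseline and 12/6/2/0 at Day 28: from 2 to 8. The minimum arises if 2 eyes go from 0 to 2 and all others stay. The maximum arises if all 6 + 2 = 8 eyes graded at Day 28 were clear at baseline and the 6 graded at baseline cleared. A search over all cross-tables with these margins gives the same limits.
- a = 0: w = b exactly. The ambiguity at a single visit vanishes for a sign that nobody has at baseline.

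**Several time points.** The schedule has eight post-dose slit-lamp examinations of the study eye: one each on Days 1, 4 and 14, and five on Day 28. One affected eye at each of two time points may be one subject or two. So even with a = 0, separate frequencies do not give the number ever affected.

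**Would the descriptive statistics of Protocol 8.2 be enough?** Only in part. The mean change equals the difference of the two means, which the frequencies already fix. In the 6-and-6 case it is 0 whether nobody or six subjects worsened. The maximum of the change would reveal that someone worsened (0 against +1), but not how many. A count of grade increases gives the number directly.

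**Baseline.** SAP section 3 puts the first dose in the study eye on Day 0, after the pressure reading at T0 + 12 hours. The Day 1 slit-lamp examination therefore follows that dose, and all five on Day 0 precede it. The SAP's Day 1 baseline for biomicroscopy is thus a post-dose value. The schedule has no Day 1 collection at all for vital signs or PK, which share the same baseline sentence.

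**The case against.** The case on the other side has real force.

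- **Worsening is not lost.** A reader might infer that ocular deterioration will be invisible in the report. The documents do not support that. Fundus worsening since Screening must be reported as an adverse event and is then tabulated by arm. Clinically significant slit-lamp worsening is reportable too, and SAP section 7 puts all data in listings. What remains is narrower: adverse event tables work by preferred term with both eyes counted once, so they show no grade change per eye, and sub-clinical slit-lamp changes appear only in listings.
- **Protocol 8.2 does not require shift tables.** A reader might infer that it does. It makes them optional, and what it states in firm terms is the display of change. The vitreous, retina, macula and choroid items are scored 0/1 and may properly be treated as qualitative, so plain counts satisfy 8.2 for them.
- **The vehicle arm helps.** Frequencies compared between randomised arms at the same visit do inform on drug effect, so the tables are not worthless. They still do not count who worsened.
- **Some signs should be nearly absent at entry.** Past uveitis, keratitis or scleritis, and recent ocular inflammation, are excluded. For cells, flare and corneal edema, a frequency at one visit should come close to an incidence. This does not carry over to lid signs, lens opacity or the optic nerve.
- **The main expected effect is covered.** Photographic conjunctival hyperemia has change from Day 0 in Appendix 2, and this point does not extend to it.

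**Conclusion.** The point holds for the ordinal slit-lamp grades and the optic nerve grade. For these, SAP 7.13 delivers less than Protocol 8.2 states, leaves the defined baselines unused, and gives summary tables from which the number of subjects who worsened cannot be derived. It is a gap in the summaries of a primary-objective measure, not a loss of data.

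The range of 0 to 6 among 20 shows what the tables leave open under assumed counts and complete data. It does not predict what this trial will find. For a sign with no baseline findings, the ambiguity at a single visit disappears.

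The change is worth making before unmasking. Otherwise whoever counts worsening from the listings must choose the threshold and the visits after seeing the results.

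**What to change.** 1. **Correct the baseline first.** In SAP section 7, set the biomicroscopy baseline to the pre-dose T0 examination on Day 0. Keep Screening for ophthalmoscopy.
2. **Add to SAP 7.13, for each slit-lamp sign and the optic nerve grade, by arm and by study and non-study eye:** n (%) with an increase of at least 1 and of at least 2 grades from baseline to the worst post-dose grade, displayed with a shift table of baseline against worst post-dose grade.
3. **For the 0/1 fundus items:** n (%) changing from normal to abnormal.
4. **Settle three definitions in the text.** For the non-study eye, count as post-dose only examinations after its first dose; the Day 4 slit-lamp examination precedes that dose. For slit-lamp hyperemia, which has a 0.5 level, say whether an increase is counted in scale steps or in units. For ophthalmoscopy, Day 28 is the only scheduled post-dose examination, so the worst grade is the Day 28 grade unless an unscheduled examination is included.

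The cost is a few extra tables from data already collected, with no change to trial conduct.
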